#### **10.2.2 Demographics and Baseline Characteristics**

##### **Treatment Cohort**

Demographics, baseline characteristics, and medical history will be summarized.

Demographic data (at Study 115B baseline) will include the following:

- Age at baseline (months)
- Age Group at Baseline (< 3 and ≥ 3 years)
- Sex (female and male)
- Ethnicity (Hispanic or Latino, not Hispanic or Latino, and not collected per local regulations)

- Race (White, Black or African American, Asian, American Indian or Alaska Native, Native Hawaiian or Other Pacific Islander, Not Collected per Local Regulations and Other)

Baseline characteristics will include the following:

- Weight (kg)
- Weight Group at Baseline (<14 kg and ≥14 kg)
- Stature (cm)
- BMI (kg/m^2)
- Weight-for-age z-score
- Stature-for-age z-score
- BMI-for-age z-score
- Sweat Chloride
- FEV1 (L)
- Percent predicted FEV1 (ppFEV1, percentage points)
- LCI2.5 and LCI5.0

Medical history will be summarized by MedDRA System Organ Class (SOC) and Preferred Term (PT). All demographic and baseline characteristic data will be listed.

### 10.2.3 Prior and Concomitant Medications

Medications used in this study will be coded by using the World Health Organization Drug Dictionary (WHODD, March 2018, Format B3 or higher) and categorized as the following:

- **Prior medication:** any medication continued or newly received before initial dosing of study drug in Study 115B.
- **Concomitant medication:** medication continued or newly received during the Treatment-emergent Period of the Current Study Period.
- **Post-treatment medication:** medication continued or newly received after the end of the treatment-emergent Period of the Current Study Period.

A given medication can be classified as a prior medication, concomitant medication, or a post-treatment medication; both concomitant and post-treatment; both prior and concomitant; prior, concomitant, and post-treatment. If a medication has a missing or partially missing start/end date or time and it cannot be determined whether it was taken before initial dosing, concomitantly, or more than 14 days after the last dose of study drug, it will be considered as prior, concomitant, and post-treatment.

Incidence of prior medications will be summarized based on the 116 Safety Set by 1) Preferred name; 2) Anatomic class (ATC) level 1, ATC level 2, and preferred name.

Incidence of concomitant medications will be summarized based on 116 Safety Set for Current Study Period by 1) Preferred name; 2) Anatomic class (ATC) level 1, ATC level 2, and preferred name.

All medications in the Current Study Period will be listed for each subject.

Details for imputing missing or partial start and/or stop dates of medication are described in [Appendix D](#).

#### **10.2.4 Study Drug Exposure**

Study drug exposure will be summarized for the Current Study Period based on 116 Safety Set.

Duration of study drug exposure is defined as: last available dose date of the Current Study Period – first dose date of the Current Study Period + 1 day, regardless of unplanned interruptions.

Duration of study drug exposure as well as number of sticks/tablets administered defined as (total number of sticks and/or tablets dispensed) – (total number of sticks and/or tablets returned) will be summarized descriptively. Additionally, the total duration of treatment exposure, defined as the sum of the subject's duration of treatment exposure and expressed in subject-years (1 subject with 48 weeks of treatment exposure is considered 1 subject-year) will be provided.

Duration of exposure will also be summarized as a categorical variable (>0 to ≤8 weeks, >8 to ≤24 weeks, >24 to ≤48 weeks, >48 to ≤72 weeks, >72 to ≤96 weeks, >96 weeks).

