#### **Safety Analysis**

All treatment-emergent AE (TEAE) summaries will be described using the incidence of TEAEs and number of events per 100 patient-years (number of events adjusted for the total duration of exposure) for the Cumulative Study Period.

Continuous safety endpoints will be summarized descriptively at each visit during the Cumulative Study Period.

For the categorical laboratory, vital, and ECG variables, the number and percentage of subjects in each category during the Treatment-emergent Period of the Cumulative Study Period will be summarized.

The safety analysis for the Cumulative Study Period will be based on the Safety Set, which will include all subjects who received at least 1 dose of study drug in Study 115B.

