## 12.3.2.4 Study Drug Exposure and Compliance

#### **Study Drug Exposure**

Duration of study drug exposure is defined as follows: last dose date of the Cumulative Study Period – first dose date of the Cumulative Study Period + 1 day, regardless of any dose interruptions.

Duration of study drug exposure as well as number of sticks administered defined as (total number of sticks dispensed) – (total number of sticks returned) will be summarized descriptively overall based on Safety Set for the Cumulative Study Period. Additionally, the total duration of treatment exposure, defined as the sum of the subject's duration of treatment exposure and expressed in subject-years, will be provided. Duration of exposure will also be summarized as a categorical variable.

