### **10.3.2.6 Analysis of Pulmonary Exacerbation-related Other Secondary Pharmacodynamic Variables**

**Time-to-first pulmonary exacerbation:** Time-to-first pulmonary exacerbation, defined as days from study drug initiation in the Study 115B to first pulmonary exacerbation, will be analyzed using Kaplan-Meier (KM) method based on the FAS for the Cumulative Study Period. Cumulative incidence of pulmonary exacerbation will be summarized for the overall group. Subjects without an exacerbation will be considered censored at the end date of the Cumulative Study Period.

**Number of pulmonary exacerbations:** The number of pulmonary exacerbations starting during the Cumulative Study Period (including both on-treatment events and events after treatment discontinuation), normalized by the time spent in the Cumulative Study Period (last date in the Cumulative Study Period – first date in the Cumulative Study Period + 1), will be summarized for the overall group based on the FAS.

**Number of CF-related hospitalizations through last visit:** The number of CF-related hospitalizations occurring during the Cumulative Study Period (including both on-treatment events and events after treatment discontinuation), normalized by the time spent in the Cumulative Study Period (last date in the Cumulative Study Period – first date in the Cumulative Study Period + 1), will be summarized for the overall group based on the FAS.

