### 10.5.1 Adverse Events

For analysis purposes, AEs will be classified as TEAEs, or post-treatment AEs.

- **TEAE:** any AE that increased in severity or that was newly developed during the Treatment-emergent Period of the Current Study Period.
- **Post-treatment AE:** any AE that increased in severity or that was newly developed after the end of the Treatment-emergent Period of the Current Study Period.

For AEs with missing or partial start dates, if there is no clear evidence that the AEs started before or after study treatment, then the AEs will be classified as TEAEs. Details for imputing missing or partial start dates of AEs are described in [Appendix E](#).

TEAE summaries will be presented using number and percentages of subjects for the Current Study Period based on 116 Safety Set.

An overview of the TEAE profile will be provided, including total number of TEAEs, with number and percentage of subjects for the following categories: 1) all TEAEs; 2) Grade 3/4 TEAEs; 3) TEAEs by relationship; 4) TEAEs by maximum severity; 5) TEAEs leading to treatment interruption; 6) TEAEs leading to treatment discontinuation; 7) serious TEAEs; 8) serious TEAEs related to study drug; and 9) TEAEs leading to death.

AE summary tables will be presented for TEAEs only and will include the following:

- All TEAEs
- Grades 3/4 TEAEs
- TEAEs by relationship to study drug
- TEAEs by maximal severity
- TEAEs leading to treatment interruption
- TEAEs leading to treatment discontinuation
- Serious TEAEs
- Serious TEAEs related to study drug
- TEAEs leading to death
- Frequently reported TEAEs ( $\geq 5\%$  at the preferred term level for the overall column)

Summaries will be presented by MedDRA SOC and PT using frequency counts and percentages (i.e., number and percentage of subjects). When summarizing the number and percentage of subjects with an event, subjects with multiple occurrences of the same AE or a continuing AE will be counted once, only the maximum severity level will be presented in the severity summaries, and the worst/highest relationship level in the relationship summaries.

In addition, listings containing individual subject data for all TEAEs leading to treatment interruption, TEAEs leading to treatment discontinuation, deaths, and SAEs will be provided separately. All AEs, including pre- and post-treatment AEs, will be presented in individual subject data listings.

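### SAP 10.2.4 counts 48 weeks of exposure as one subject-year, so total exposure is reported 8.7% above calendar subject-years

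*SAP*

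**What the plan says.** SAP Section 10.2.4 (Study Drug Exposure) defines each subject's duration as "last available dose date of the Current Study Period – first dose date of the Current Study Period + 1 day, regardless of unplanned interruptions", which is a count of calendar days. It then asks for "the total duration of treatment exposure, defined as the sum of the subject's duration of treatment exposure and expressed in subject-years", and fixes the unit in parentheses: "1 subject with 48 weeks of treatment exposure is considered 1 subject-year".

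Protocol Section 12.3.2.4 contains the same request, for a total "defined as the sum of the subject's duration of treatment exposure and expressed in subject-years, will be provided". It attaches no 48-week conversion.

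Three other places show where the total could or could not be used:

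- SAP Section 10.5.1: "TEAE summaries will be presented using number and percentages of subjects for the Current Study Period based on 116 Safety Set". It specifies no rate per patient-year.
- SAP Section 10.3.2.6: pulmonary exacerbations and CF-related hospitalizations are "normalized by the time spent in the Cumulative Study Period", measured from first to last date, with no 48-week rule.
- Protocol synopsis (Safety Analysis) and Section 12.3.4.1: TEAEs are to be shown per 100 patient-years, for the Cumulative Study Period. The SAP does not carry this forward.

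**The concern.** The SAP adds up calendar days, divides by a period shorter than a year, and gives the result the ordinary name for calendar person-time. Nothing in the SAP requires the output table to carry the 48-week definition, so a reader of the table would take the figure as calendar years.

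The primary objective is long-term safety, and total subject-years is the figure that says how much treated time supports it. The convention makes that figure larger than it is.

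There is also a route to a wrong rate, although the SAP does not plan one. Section 10.5.1 reports the total number of TEAEs for the 116 Safety Set over the Current Study Period, and Section 10.2.4 reports subject-years for the same set and period. Someone wanting the exposure-adjusted rate that the protocol described could divide one by the other. The result would be too low, which is the reassuring direction.

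**Working it through.** **Inputs**

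- Length of one subject-year under the SAP: 48 weeks (SAP 10.2.4).
- Planned treatment: 96 weeks (Protocol 9.1.2.1).
- Expected enrolment: 50 (SAP 7.2). This reproduces: 56 × (1 − 0.10) = 50.4.
- Length of a calendar year: 365.25 days, with 365 days and 52 weeks (364 days) as variants. The documents give no year length, so this is the reviewer's input.

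**Step 1: the SAP's unit in days.** 48 × 7 = 336 days. The SAP's visit windows (Appendix C) agree. Counting from first dose as Day 1, Week 48 has target day 337 and Week 96 has target day 673, so 336 and 672 days have elapsed.

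**Step 2: the overstatement.** SAP subject-years = total days / 336. Calendar subject-years = total days / year length. Total days cancel in the ratio, so the excess is year length / 336 − 1, whatever the number of subjects or their actual durations.

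| Year length | Year length / 336 | Excess in total subject-years |
|---|---|---|
| 365.25 days | 1.0871 | 8.7% |
| 365 days | 1.0863 | 8.6% |
| 364 days (52 weeks) | 1.0833 | 8.3% |

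**Step 3: what it looks like in the report.** The subject numbers and durations in the last two rows are assumptions for illustration.

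| Case | Total days | SAP rule (/336) | Calendar (/365.25) |
|---|---|---|---|
| One subject completing 96 weeks | 672 | 2.00 | 1.84 |
| 50 treated, all completing 96 weeks (upper case) | 50 × 672 = 33,600 | 100.0 | 92.0 |
| 40 treated, averaging 72 weeks | 40 × 504 = 20,160 | 60.0 | 55.2 |

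**Step 4: effect on a rate, if one were formed with this total.** 336 / 365.25 = 0.920, so the rate would be 8.0% too low. For example, with 100 events (assumed) in the 33,600-day case, the rate is 100.0 per 100 SAP subject-years and 108.7 per 100 calendar subject-years.

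**The case against.** The strongest reply is that this is a disclosed definition and not a miscalculation. The conversion stands in the same sentence as the unit, anyone who reads it can convert exactly, and per-subject exposure is listed (SAP 10.2.5), so calendar person-time can be recovered.

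It may also be deliberate. The exposure categories in SAP 10.2.4 include cut-points at 24, 48, 72 and 96 weeks. Protocol 9.3.2 puts combined treatment over both studies at up to about 2.5 years: 24 + 96 = 120 weeks, which is exactly 2.5 at 48 weeks per year but 840 / 365.25 = 2.30 calendar years.

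Finally, no planned result changes. Safety is descriptive, TEAEs are counts and percentages of subjects, duration categories are in weeks, and the 8% effect on rates arises only if someone forms a rate that the SAP does not specify.

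Much of this stands. The convention is not hidden, the effect is limited to one descriptive total, and the rate effect is conditional. But disclosure in the SAP does not correct a table entry labelled subject-years. The protocol's figure is an approximation and establishes no convention. Being able to recompute the total from listings is no reason to print it in a misleading unit.

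**Conclusion.** The point holds. As written, the SAP will report total exposure 8.7% above calendar subject-years, taking a year as 365.25 days; over the usual year lengths the range is 8.3% to 8.7%. The size rests on no assumption about enrolment, dropout or adherence. The absolute figures above do rest on assumed numbers and durations.

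The error is confined to the total subject-years line. Duration categories, per-subject listings, TEAE percentages and the time-normalized event counts are not shown to be affected. It should be corrected because it is certain, runs in one direction, and concerns the exposure figure behind the primary objective. It does not threaten any planned conclusion.

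**What to change.** In SAP Section 10.2.4, replace the 48-week parenthesis with a definition of subject-years as the sum of exposure days divided by 365.25. If a rate per patient-year is reported for this study, use the same year length for it.

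If the sponsor wants to keep the 48-week unit, the minimum is to label it in the output as 48-week years and show calendar subject-years beside it.

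The cost is one SAP line and one program constant. Reported exposure becomes about 8% smaller. SAP Section 4 has the plan finalized before database lock and any later change documented in the clinical study report, so the correction can be made at either stage.

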#### **10.2.5 Study Drug Compliance**

Study drug compliance will be summarized for the Current Study Period based on 116 Safety Set.

Study drug compliance will be calculated for the Current Study Period as follows:  $100 \times (1 - [\text{Total number of days of study drug interruption in Current Study Period}] / [\text{Duration of study drug exposure in Current Study Period} + \text{Total number of days study drug interrupted after last dose in Current Study Period, if any}])$ . The total number of days of study drug interruption is defined as the sum of (number of days of each study drug interruption in the Current Study Period), where number of days of each study drug interruption is defined as the interruption end date – the corresponding interruption start date + 1.

Treatment compliance percentages will be summarized descriptively (number, mean, SD, median, minimum, and maximum). The number and percentage of subjects whose compliance is <80% or ≥80% will be also be summarized.

In calculating the total number of days of study drug being interrupted, only the interruptions with duration of ≥3 days will be considered. An interruption with duration of < 3 days will not be considered in the calculation.

Study drug exposure and compliance data for each subject will also be listed.

## **10.2.6 Important Protocol Deviations**

IPDs will be identified from the clinical database and/or site deviation log. Important protocol deviations will be provided as a subject data listing, indicating the source (clinical database versus site deviation log). All potential IPDs from both sources will be reviewed by the study team before the final database lock to determine IPD status.

The rules for identifying programmable IPDs based on the clinical database are defined in [Appendix I](#).

IPDs will be provided as a subject data listing based on the 116 All Subjects Set.

## **10.3 Pharmacodynamic Analysis**

### **10.3.1 Analysis of Primary Endpoints**

Not applicable.

### **10.3.2 Analysis of Secondary Pharmacodynamic Endpoints**

#### **10.3.2.1 Absolute Change from Baseline in Sweat Chloride**

For each subject and at each time point, 2 sweat chloride measurements will be collected: 1 from the right arm and 1 from the left arm. Of the 2 measurements, only the sweat chloride value obtained from a sample volume  $\geq 15$   $\mu\text{L}$  will be included in any analysis (i.e., a sample volume of 15  $\mu\text{L}$  is required for testing and therefore any samples with volumes  $< 15$   $\mu\text{L}$  will not be included in the analysis). The sweat chloride results for the left and right arms will be averaged and used in the analysis if the sweat chloride values for the left and right arms are both  $\geq 15$   $\mu\text{L}$ ; if only 1 arm is  $\geq 15$   $\mu\text{L}$ , then only that value will be used. Any sweat chloride values outside of the reportable range (i.e.  $< 10$  mmol/L or  $> 160$  mmol/L) will not be included in the analysis.

Raw values and absolute change from parent study baseline in sweat chloride at each visit in the Current Study Period (including all measurements from Study 116, including the Safety Follow-up Visit of Study 116, both on-treatment measurements and measurements after treatment discontinuation), will be summarized for the overall group based on 116 FAS. Descriptive statistics including number of subjects, mean, SD, SE, median, minimum, and maximum will be provided for the absolute change from parent study baseline. In addition, the 95% CI and the within-group *P* value based on Normal approximation will be provided. The mean (95% CI) of the absolute change from parent study baseline will be plotted.

#### **10.3.2.2 Absolute Change from Baseline in BMI/BMI-for-Age Z- score**

BMI z-score will be calculated by using Centers for Disease Control and Prevention (CDC) growth charts. The BMI z-score will be calculated as follows:

$$z = \begin{cases} \frac{\left(\frac{X}{M}\right)^L - 1}{LS} & , \quad L \neq 0 \\ \frac{\ln\left(\frac{X}{M}\right)}{S} & , \quad L = 0 \end{cases}$$

Where  $X$  is the derived BMI value in  $\text{kg}/\text{m}^2$  based on the raw weight and raw height and  $L$ ,  $M$ , and  $S$  are selected from the CDC BMI-for-age chart by subject sex and age. The BMIAGE file contains these parameters by sex (1=male, 2=female) and age; it is available at: [http://www.cdc.gov/growthcharts/percentile\\_data\\_files.htm](http://www.cdc.gov/growthcharts/percentile_data_files.htm). Additionally, SAS code for calculating percentiles and z-scores is available at: [http://www.cdc.gov/growthcharts/computer\\_programs.htm](http://www.cdc.gov/growthcharts/computer_programs.htm).

NOTE: The CDC BMI-for-age charts are designed for use in pediatric populations (2 to 20 years of age).

Raw values and absolute change from parent study baseline in BMI and BMI-for-age z-score at each visit in the Current Study Period will be summarized descriptively. The 95% CI based on Normal approximation will also be provided. The mean (95% CI) of the absolute change from parent study baseline will be plotted.

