Optional LCI Assessment: LCI is a measure of ventilation inhomogeneity that is based on tidal breathing techniques that have been evaluated in patients as young as infants.  LCI correlates with FEV1 in its ability to measure airway disease in patients with mild to moderate lung disease but can also detect lung disease at an earlier stage than spirometry.  Data from Study VX10-770-106 in subjects with CF with an FEV1>90% showed LCI to be a more sensitive outcome measure than FEV1. Given the potential advantages of a more sensitive measurement during the early stages of disease progression, LCI will be used in this study. As with spirometry testing, performing LCI assessments in young children can be difficult.  Therefore, only subjects who were  $\geq$ 3 years of age at screening in Study 115B and who consent/assent to the optional LCI Substudy will undergo the LCI assessments. LCI will be done only at selected sites that have the capability to perform these assessments.

Exocrine Pancreatic Function: The pancreas is one of the earliest and most seriously affected organs in patients with CF who are homozygous for *F508del*, a high fraction of which develop pancreatic insufficiency.

- FE-1: FE-1 is a diagnostic measure of pancreatic exocrine sufficiency, with a lack of elastase output in stool being considered indicative of CF (<200 μg/g). The increasing use of FE-1 in the clinic is a result of the ease of collecting samples for its assessment and the establishment of diagnostic cut-offs for pancreatic exocrine function. FE-1 represents a feasible measure to evaluate exocrine pancreatic function during the study, with the hypothesis that rescue of pancreatic function will result in an increase in FE-1 levels.
- IRT: Trypsinogen is a protein produced by the pancreas that can be detected in the blood via the IRT assay and is used in clinical practice for neonatal screening test for CF, wherein elevated levels are associated with disease. Blood samples for IRT testing will be collected at multiple time points to evaluate potential changes in exocrine pancreatic function during the Treatment Period.

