## **7.2 Sample Size and Power**

No formal sample size calculations have been performed.

This is a long-term extension study that will enroll subjects rolled over from Study 115B.

Approximately 56 subjects were potentially eligible to be enrolled in this rollover study. Assuming a 10% dropout rate in Study 115B, 50 subjects are expected to enroll in this study.

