### **8.1 Efficacy Sets**

**Full Analysis Set (FAS):** The FAS will include all subjects who were enrolled and exposed to any amount of study drug in Study 115B.

**116 Full Analysis Set (116 FAS):** The 116 FAS will include all subjects who were enrolled and exposed to any amount of study drug in Study 116 Treatment Cohort.

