### **10.3.2.5 Absolute change from Baseline in LCI2.5 and LCI5.0**

The LCI assessment at scheduled visits will be performed in multiple replicates. The LCI values at each visit included in the analysis will be the value calculated from the technically acceptable washout replicates.

When there is only one LCI value considered acceptable by the LCI central reader, the value will NOT be used. The assessment for that subject at the corresponding visit will not be included in the analysis; when there are at least 2 LCI values considered acceptable by the LCI central reader, the arithmetic mean of the values from the accepted trials will be calculated as the value at the corresponding visit.

LCI2.5 and LCI5.0 will be analyzed in a similar way to BMI and BMI-for-age z-score.

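### The 95% CIs and the sweat chloride P value rest on a Normal approximation with an estimated SD: negligible at about 50 subjects, but intervals are too narrow where per-visit n is small (LCI, Safety Follow-up Visit)

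*SAP*

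**What the plan says.** **Sweat chloride.** SAP 10.3.2.1 summarises change from the parent-study baseline at each Study 116 visit, including the Safety Follow-up Visit, in the 116 FAS. The spread comes from the data: "Descriptive statistics including number of subjects, mean, SD, SE, median, minimum, and maximum will be provided for the absolute change from parent study baseline". A 95% CI is added, and the within-group P "value based on Normal approximation will be provided".

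**BMI and BMI-for-age z-score.** SAP 10.3.2.2 gives a CI and no P value: "The 95% CI based on Normal approximation will also be provided". Mean changes are plotted with these intervals.

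**Weight, stature and LCI.** SAP 10.3.2.3 to 10.3.2.5 refer back to BMI. For example, LCI2.5 and LCI5.0 "will be analyzed in a similar way to BMI and BMI-for-age z-score".

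**Protocol.** Section 12.3.3.2.1 has the same Normal-approximation wording for sweat chloride and extends that summary to the growth and LCI endpoints. The SAP therefore follows the protocol on the reference distribution.

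**Numbers.** SAP 7.2 states: "Approximately 56 subjects were potentially eligible to be enrolled in this rollover study". It continues: "Assuming a 10% dropout rate in Study 115B, 50 subjects are expected to enroll in this study". Neither document gives a size for the LCI subset or for the group attending the Safety Follow-up Visit.

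**The concern.** When a mean change is divided by a standard error estimated from the same sample, its exact reference distribution under normality is Student's t with n-1 degrees of freedom, not the standard Normal. A z multiplier ignores the uncertainty in the SD. The interval is then too short and the P value too small at every n, and the gap grows as n falls.

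The documents make small n likely in two places:

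- **LCI.** The substudy is optional and limited to children at least 3 years old at Study 115B screening. Protocol 9.3.3 adds: "LCI will be done only at selected sites that have the capability to perform these assessments". SAP 10.3.2.5 drops any visit with only one acceptable replicate.
- **Safety Follow-up Visit.** Protocol 9.1.2.2 requires it only for certain subjects who terminate or interrupt treatment, and waives it for those moving to commercial drug. Sweat chloride and LCI are both scheduled there.

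Week 96 may also fall below the enrolled number. SAP 10.2.1 provides for subjects leaving early for commercial drug, sweat chloride and LCI are not scheduled at the ETT Visit, and SAP 10.1 does not impute missing data.

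What is at stake is whether an interval labelled 95% has about 95% coverage in these small groups.

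**Working it through.** **1. The plan's own figure.** Inputs are 56 potentially eligible and 10% dropout (SAP 7.2). 56 × (1 − 0.10) = 50.4, which reproduces the stated 50. This is an expectation, not a ceiling. The 116 FAS counts only the Treatment Cohort ("The 116 FAS will include all subjects who were enrolled and exposed to any amount of study drug in Study 116 Treatment Cohort"), so the per-visit n may be lower.

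**2. Formulas.** Take the plain reading, mean ± 1.960 × SD/√n with the sample SD, and assume normally distributed changes.

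- Ratio of t width to z width = t(0.975, n−1) / 1.960
- Actual coverage of the z interval = 2 × F(1.960) − 1, where F is the t distribution function with n−1 df
- Two-sided type I error of the z test = 1 − coverage

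**3. Results.**

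| n | Source of n | t multiplier | t interval wider by | Coverage of z interval |
|---|---|---|---|---|
| 56 | SAP 7.2, potentially eligible | 2.004 | 2.2% | 94.5% |
| 50 | SAP 7.2, expected | 2.010 | 2.5% | 94.4% |
| 30 | assumed | 2.045 | 4.3% | 94.0% |
| 20 | assumed | 2.093 | 6.8% | 93.5% |
| 10 | assumed | 2.262 | 15.4% | 91.8% |

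As an example, at n=50 the ratio is 2.0096 / 1.960 = 1.025, and at n=10 it is 2.2622 / 1.960 = 1.154.

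**4. P value.** In the SAP this concerns sweat chloride only. At n=50 the type I error is 5.6% instead of 5%.

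**The case against.** **The SAP never writes 1.96 or names a quantile.** This is true. The phrase could describe a t interval that assumes normality of the mean change. A reader might infer that a z interval is proven, but the text does not go that far: z is the plain reading, not a stated fact. If t was intended, the same edit removes the ambiguity.

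**The effect is trivial where the documents give an n.** This stands. At 50 subjects the loss is about 0.6 percentage points of coverage. It would be wrong to say that the growth and sweat chloride intervals are materially too narrow at full n.

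**The larger figures rest on assumed sizes.** This also stands. The documents make small groups likely but do not say how small, and at n=30 coverage is still 94.0%.

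**A reader might attach an inflated type I error to LCI.** At n=10 a z test would have 8.2% (100% − 91.8%). The SAP does not support that use, because it sends LCI to the BMI method, which has a CI and no P value. The protocol's cross-reference to the sweat chloride summary could be read more widely, but the SAP's specification is the narrower one.

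**No decision depends on these intervals.** SAP 10.1 disclaims hypothesis testing, there is no sample size calculation, and the primary endpoint is safety. Because n, mean and SE are reported, a reader could rebuild a t interval. This lowers the importance but does not make a z quantile right for small groups that will be tabulated and plotted as 95% intervals.

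**The t interval is exact only under normality.** This is correct, and the documents do not show that the changes are normal. It still accounts for the estimated SD, which z does not.

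**Conclusion.** The point holds as a minor correction. On the plain reading, the plan uses a z quantile with an estimated SD and so gives intervals that are slightly too narrow. The loss is negligible at the expected 50 subjects. It becomes noticeable only where few children contribute, with about 1.5 points of coverage lost at n=20 and about 3 at n=10.

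This rests on three assumptions: that Normal approximation means z, that changes are roughly normal, and that the LCI or Safety Follow-up n falls in the range of 10 to 30. Only descriptive secondary endpoints are affected. The material does not support a claim of seriously misleading intervals across the study, or of inflated LCI testing.

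**What to change.** In SAP 10.3.2.1 (CI and P value) and 10.3.2.2 (CI), replace 'based on Normal approximation' with 'based on the one-sample t distribution (n-1 df)'. The cross-references in 10.3.2.3 to 10.3.2.5 then carry it to weight, stature and LCI without further edits. Record it in the SAP as a change from Protocol 12.3.3.2.1, so that the two documents do not differ without explanation.

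The cost is one phrase in two places and slightly wider intervals. No new data or design change is needed.
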